## 6.5 IMAGING CONTRAST MEDIA

### Mangafodipir

Mangafodipir trisodium (manganese dipyridoxyl diphosphate, MnDPDP; IC Targets, Norway) 0.05 mmol/mL solution for intravenous infusion. Each mL contains 37.85 mg of anhydrous mangafodipir trisodium, 0.05 mmol (50 µmol), equivalent to 35.55 mg of mangafodipir. 10 mL contains 378.5 mg of anhydrous mangafodipir trisodium, 0.50 mmol (500 µmol), equivalent to 345.5 mg of mangafodipir. The standard dose of Mangafodipir will be 5ml although this will

be subject to the results of an ongoing comparison study being undertaken at the Edinburgh Royal Infirmary.

The manganese will be administered by intravenous infusion over a period of approximately 10-15 minutes (0.4-1.2mL/min), during the cardiac MRI scan.

## 7 STUDY ASSESSMENTS

### 7.1 STUDY ASSESSMENTS

All patient's eligible for the study will have informed consent taken as well as a standardised clinical assessment. For patients in study 1 this will be carried out in the Clinical Research Facility or on the participants' inpatient ward. For patients in study 2 this will be carried out in the Clinical Research Facility. Participants will be reimbursed for travel costs to the Clinical Research Facility, up to a value of £50 per participant.

The different aspects of the study assessments are summarised in the table below:

Assessment	Description	Time required	Associated risks
Consent	The co-investigator will explain the study to potential participants with adequate opportunity for the participant to ask questions. If the participant agrees they will be asked to sign a consent form.	10 minutes	Nil significant
Medical history and physical examination	The co-investigator will check that patients don't have any study eligibility contraindications. They will also check the patients' past medical history, medications and allergies and will record their height, weight, heart rate and blood pressure and perform a physical cardiovascular examination.	15-20 minutes	Nil significant
Blood tests	A needle will be inserted to take blood tests to ensure the patient is eligible to take part in the study as well as to assess their current clinical cardiac status and for storage of samples.	10 minutes	Pain from needle used for taking blood tests

Patient questionnaire	Participants will be asked to complete a questionnaire about their symptoms and quality of life	10 minutes	Nil significant
ECG	We will perform an electrical tracing of the participants' hearts.	10 minutes	Irritation from sticky pads used for ECG
Cannula	A small needle will be inserted into the participant's arm, This will allow us to inject the manganese contrast.	10 minutes	Pain related to needle
Urine pregnancy test	This will be performed in female participants of child-bearing potential to ensure study eligibility.	5 minutes	Nil significant
Echocardiogram	We will perform an ultrasound scan of the participants' hearts.	20 minutes	Nil significant
6-minute walk test	We will ask the participant to walk on the flat for 6 minutes whilst monitoring their oxygen saturations via pulse oximetry.	6 minutes	Nil significant
MEMRI scan	An MRI scan of the heart will be performed and the patient will be injected with manganese contrast.	1 hour	Small risk of allergic reaction to manganese Claustrophobia
Randomisation to medication	Participants will be randomised to medication	10 minutes	Nil significant
Pill counting	We will count the participants' study medications.	5 minutes	Nil significant

## 7.2 STUDY VISITS

Study 1 participants will undergo 4 study visits if they are randomised to no medication and 6 study visits if they are randomised to medication. Study 2 participants will undergo 7 study visits in total. Healthy volunteers will attend for 2 study visits. The below tables summarise the different assessments participants will undergo at each study visit:

### Study 1

Assessment	Screening and Randomisation visit	1 week (Patients on Bisoprolol/ Valsartan)	2 weeks (Patients on Bisoprolol/ Valsartan)	4±1 weeks	3±1 months
Assessment of Eligibility Criteria					
Written informed consent					
Demographic data, contact details					
Clinical assessment as per study protocol					
Blood samples as per study protocol					
Patient questionnaires as per study protocol					
12-lead ECG					
Transthoracic Echocardiogram					
6-minute walk test					
Urinary pregnancy test					
Manganese-enhanced Cardiac Magnetic Resonance Imaging					
Randomised allocation to Bisoprolol, Valsartan or no medication					
Adjustment of medication dose					
Stop medication					
Pill counting					

## Study 2

Assessment	Screening and Randomisation Visit	1 week (Patients on sacubitril/valsartan)	2 weeks (Patients on sacubitril/valsartan)	3±1 months	4±1 months	1 week (Patients on sacubitril/valsartan)	2 weeks (Patients on sacubitril/valsartan)	7±1 months
Assessment of Eligibility Criteria								
Written informed consent								
Demographic data, contact details								
Clinical assessment as per study protocol								
Blood samples as per study protocol								
Patient questionnaires as per study protocol								
12-lead ECG								
Transthoracic Echocardiogram								
6-minute walk test								
Urinary pregnancy test								
Manganese-enhanced Cardiac Magnetic Resonance Imaging								
Randomised allocation to Sacubitril/Valsartan or Dapagliflozin								
Adjustment of medication dose								
Stop medication								
Pill counting								

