#### 6.1.2 Doses and treatment regimens

Patients in study 1 will be randomised 1:1:1 to no treatment, or open-label valsartan or bisoprolol.

Patients in study 2 will receive 3 months treatment with combination sacubitril and valsartan and dapagliflozin 10 mg in random order. This will be separated by a one-month medication “wash out period.”

Medications will be prescribed on a research specific prescription form by a co-investigator in the Clinical Research Facility. The medication will then be dispensed “off the shelf” from the Royal Infirmary of Edinburgh pharmacy department.

Randomisation will take place by block randomisation. An unbiased colleague will create the blocks for randomisation and the study investigators will be blinded to the blocks until the point of randomisation.

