### **7.5 CLINICAL ASSESSMENT**

This will involve checking participants' height, weight, heart rate and blood pressure. The co-investigator will perform a physical clinical examination of the participants' cardiovascular system.

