### **7.7 URINE PREGNANCY TEST**

This will be performed in female participants of child bearing potential.

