## 8 DATA COLLECTION

### *Clinical Assessment*

Any changes in medication, any hospital admission or any clinical symptoms will be assessed at the study visit by the investigator.

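### Study 2's table has no pregnancy test at the 4±1 month visit, so the second drug starts on a test nominally one month old

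*Protocol*

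**What the plan says.** Study 2 is a two-period cross-over of sacubitril/valsartan and dapagliflozin, three months each in random order. Of the interval between them, Protocol section 6.1.2 says "This will be separated by a one-month medication" washout. The Study 2 table in section 7.2 fixes what happens at each visit:

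- "Randomised allocation to Sacubitril/Valsartan or Dapagliflozin" is ticked at the screening and randomisation visit and at 4±1 months.
- "Urinary pregnancy test" is ticked at the screening and randomisation visit, at 3±1 months and at 7±1 months. The manganese MRI row has the same three ticks.
- Stopping medication is ticked at 3±1 and 7±1 months.
- At 4±1 months only clinical assessment, blood samples and allocation are ticked.

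Section 7.1 gives the purpose of the test: "This will be performed in female participants of child-bearing potential to ensure study eligibility". Section 7.7 says who is tested but not when: "This will be performed in female participants of child bearing potential". Section 4.3 lists current pregnancy as an exclusion. The assessment of eligibility criteria is ticked only at screening.

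**The concern.** The second allocation is a new exposure to a different drug after a drug-free month. At the first allocation the table places a pregnancy test in the same column. At the second it does not, and the protocol gives no reason for the difference. The test row appears to follow the scanner: it matches the MRI row in the Study 1 and Study 2 tables, and the healthy-volunteer table, which involves no drug, ticks both in its one column. That arrangement covers the first drug start because MRI and allocation share a column. It misses the second because the washout separates them.

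At stake is a participant-safety check. Current pregnancy bars entry, yet no scheduled test repeats that check before the second drug. A pregnancy beginning in the washout would not meet a scheduled test until the second course is ending. Sections 4.2 and 4.3 set no upper age limit and no contraception requirement, so the entry criteria themselves do not close the gap.

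**Working it through.** **Inputs**

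- Pregnancy tests at months 0, 3 and 7 (section 7.2, Study 2 table).
- Drug allocation at months 0 and 4 (same table).
- Windows of ±1 month on the visits at months 3, 4 and 7 (same table).
- Washout of one month and treatment of three months per period (section 6.1.2).
- 40 participants in Study 2 (section 4.1.2).
- 90% of those affected by the disease are women, predominantly aged 50–74 (section 1.1.1).

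**The plan's own timing.** First drug stopped at month 3, second allocated at month 4: 4 − 3 = 1 month, which is the stated washout. Then 4 + 3 = 7 months, which is the final visit. The table and section 6.1.2 agree.

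**Age of the test when each drug is allocated**

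| Allocation | Last scheduled test | Age, nominal |
|---|---|---|
| First (month 0) | month 0 | 0 − 0 = 0 months, as tabulated |
| Second (month 4) | month 3 | 4 − 3 = 1 month |

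The month-3 test shares a column with stopping the first drug. If the one-month washout is kept, the second test age is therefore 1 month whatever the actual visit dates. If instead the two windows are used independently, month 3 falls at 2–4 and month 4 at 3–5. The longest gap is 5 − 2 = 3 months and the shortest is 0 with visits kept in order. The range 0–3 months arises only if the washout is not held at one month.

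**Interval between the tests on either side of the second drug start.** 7 − 3 = 4 months nominally. With windows it runs from 6 − 4 = 2 to 8 − 2 = 6 months.

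**Could anything else at month 4 stand in for the test?**

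- Clinical assessment (section 7.5) is height, weight, heart rate, blood pressure and, in its words, "The co-investigator will perform a physical clinical examination of the" cardiovascular system.
- Blood samples (section 7.6) are renal, haematological and liver tests, NT-proBNP and stored samples. No pregnancy assay is named.
- Section 8 adds a review: "Any changes in medication, any hospital admission or any clinical symptoms will be assessed at the study visit by the investigator". This might bring a pregnancy to light, but it is not a test.

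**Visit count.** Section 7.2 states "Study 2 participants will undergo 7 study visits in total". The table gives any one participant screening (1), two titration visits in the sacubitril/valsartan period only (2), and months 3, 4 and 7 (3): 1 + 2 + 3 = 6. The screening column may therefore merge two visits, which is why the zero for the first drug is marked as tabulated. The gap at the second drug is unaffected.

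**Reach.** 40 × 0.90 = 36 women, if the disease-wide share applies. The share of child-bearing potential is not given. Assuming 0–10%, the number is 36 × 0 = 0 to 36 × 0.10 = 3.6, that is 0 to about 4 women.

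**After the fix.** With a test at the month-4 visit, its age at the second allocation is 4 − 4 = 0 months, as at the first.

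**The case against.** The case for leaving the schedule alone has five parts.

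1. **The protocol breaks no promise of its own.** Section 7.1 ties the test to study eligibility, which is assessed only at screening, and no section undertakes to test before each drug. This stands: the point is a scheduling gap and not a contradiction.
2. **No drug-related harm in pregnancy is documented.** The side-effect table in section 6.4.1 lists none, and section 4.3 gives reasons for several drug-related exclusions but none for pregnancy. The exclusion could concern the scan or the contrast agent. This also stands, so the argument rests only on the protocol treating pregnancy as a bar to entry. It limits how strongly the point can be put, but it does not explain why a check that accompanies the first drug is absent at the second.
3. **The comparison with the first drug is uncertain.** If screening is really two visits, the first drug may also start some time after its test. That is possible and would weaken the contrast, but the last test before the second drug would still fall at month 3.
4. **Part of the schedule could not be read.** The Study 2 flow chart in section 3 was not available for this check. It is described as a summary, and the explicit table would still need correcting if the two differed.
5. **The gain is small.** Each period has about three months of dosing without a test, and the fix does not shorten that. It covers only pregnancies arising around the washout, possibly in nobody, and the symptom review at month 4 might detect some of them anyway. This is fair and sets the importance of the point, but the cost is smaller still.

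**Conclusion.** The point holds as a minor, inexpensive safety improvement. As tabulated, the second Study 2 drug starts on a pregnancy test that is nominally one month old and was taken before the washout. The next scheduled test is nominally four months after that one. The one-month figure assumes that the washout is kept; 0–3 months applies only if it is not.

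The estimate of 0 to about 4 women affected rests on the 90% female share in section 1.1.1 applying to this cohort and on an assumed 0–10% of child-bearing potential, which the protocol does not give. Nothing in the endpoint, power or analysis changes.

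**What to change.** In the Study 2 table of section 7.2, tick the urine pregnancy test at the 4±1 month visit for women of child-bearing potential. State there or in section 7.7 that a negative result is required before the second drug is dispensed.

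The visit already takes place. The cost is one additional urine test for the few women concerned, which section 7.1 lists as taking 5 minutes with no significant risk. Nothing else in the design needs to move.

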## Healthy Volunteers

Assessment	Visit 2 (2 weeks)
Assessment of Eligibility Criteria	
Written informed consent	
Demographic data, contact details	
Clinical assessment as per study protocol	
Blood samples as per study protocol	
Patient questionnaires as per study protocol	
12-lead ECG	
Transthoracic echocardiogram	
6-minute walk test	
Urine pregnancy test	
Manganese-enhanced Cardiac Magnetic Resonance Imaging	

### **7.3 STUDY SCREENING**

For Study 1, potential participants will be identified by the co-investigator either whilst the participant is still in hospital or shortly after discharge. A member of the study team will provide an information sheet if the participant is interested in taking part in the study.

For Study 2, the co-investigator will identify patients within the NHS Lothian Health Board via the Scottish National Takotsubo registry. Participants will also be identified within the NHS Greater Glasgow and Clyde Health Board by their usual clinical care team.

Healthy volunteers will be recruited via an advertisement process.

An anonymised screening log will be maintained by the co-investigator.

### **7.4 DEMOGRAPHIC DATA**

This will include name, initials, age, sex, height, weight, CHI number, telephone number, address, postcode and email address if available.

### **7.5 CLINICAL ASSESSMENT**

This will involve checking participants' height, weight, heart rate and blood pressure. The co-investigator will perform a physical clinical examination of the participants' cardiovascular system.

### **7.6 BLOOD SAMPLES**

This will include blood sampling for standard biochemical and haematological analyses (Urea and Electrolytes, Full Blood Count and Liver Function Tests) to check participants are eligible and safe to take part in the study. Further samples will be taken for U and Es for safety monitoring purposes for participants randomised to Valsartan and Sacubitril/Valsartan. An N-terminal pro-brain natriuretic peptide will be taken for research purposes.

Furthermore, three blood samples will be taken from each participant and stored for potential future biomarkers.

### **7.7 URINE PREGNANCY TEST**

This will be performed in female participants of child bearing potential.

## **7.8 PATIENT QUESTIONNAIRES**

Quality of life, symptoms, physical and social function will be recorded using the Kansas City Cardiomyopathy Questionnaire (KCCQ-12), Health Status (EQ-5D-5L) and the Patient-Reported Outcomes Measurement Information System short modules on Anxiety, Depression, Fatigue and Physical Function.

## **7.9 12-LEAD ECG**

An electrical recording of the participants' hearts will be undertaken.

## **7.10 6-MINUTE WALK TEST**

Participants will be asked to walk on the flat for 6 minutes whilst having their oxygen saturations monitored via a pulse oximeter.

## **7.11 ECHOCARDIOGRAPHY**

All study participants including healthy volunteers will be studied with a standard 3 MHz transducer and 2- dimensional, M-mode, Doppler and colour Doppler measurements taken. Ejection fraction will be quantified using the modified Simpson's technique and regional wall motion abnormalities assessed. If not performed as part of standard of care (whilst the participant is in hospital), we will organise a study specific transthoracic echocardiogram to be performed at visit 2 or as soon as possible as when is convenient for the participant.

## **7.12 MANGANESE-ENHANCED CARDIAC MAGNETIC RESONANCE IMAGING**

Magnetic resonance imaging will be performed at the Edinburgh Imaging Facility in the Queen's Medical Research Institute, University of Edinburgh.

## **7.13 STORAGE AND ANALYSIS OF SAMPLES**

Blood samples for storage will be frozen (-70 degrees Celcius) and kept for a minimum of five years. They will be stored in a locked freezer in appropriately secured premises in the Laboratory at Edinburgh Royal Infirmary. The retained blood samples and participants data (including MRI images) will be used for secondary studies separate to this study as hypotheses arise. Anonymised blood samples may be sent to other academic institutions within the UK for analysis. Participants will be asked for their consent for storage of samples and use in other studies at the first study visit as part of the consent process.

## 8 DATA COLLECTION

### *Clinical Assessment*

Any changes in medication, any hospital admission or any clinical symptoms will be assessed at the study visit by the investigator.

### *Blood Sampling*

Blood samples will be collected as per standard clinical care. The results will be uploaded onto the patients electronic NHS Lothian medical record.

### *Electrocardiogram*

Electrocardiograms will be recorded as per standard clinical care and uploaded onto the patient's electronic NHS Lothian medical record.

### *Echocardiography*

Echocardiography will be performed according to standard clinical care. Echocardiograms will be uploaded to the EchoPAC data storage system as part of the patient's electronic NHS Lothian medical record.

### *Cardiac Magnetic Resonance Imaging with Gadolinium*

Cardiac magnetic resonance imaging will be performed according to standard clinical care and uploaded onto the National PACS system.

### ***Cardiac Magnetic Resonance Imaging with Manganese***

All images will be acquired with a 3T Siemens scanner. A 60-channel cardiac coil will be used to perform standard cardiac imaging sequences (breath-held, electrocardiogram-gated) for 2-chamber, 4-chamber, long axis and short axis views of the heart. This will provide standard assessment of cardiac volumes, mass, and function including left ventricular ejection fraction and regional wall motion abnormalities. Myocardial T1 will be measured serially for 40-60 min after intravenous infusion of mangafodipir (5 mmol/kg, 1 mL/min; IC Targets, Norway). T1 imaging will be performed with Modified Look-Locker Inversion recovery (Siemens Healthineers) in both short axis (base, mid-cavity) images of the heart (4-chamber and 2-chamber views to capture the apex). Scanner-generated T1 maps will be analysed to quantify T1 within regions of interest.

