## 10.2 PROPOSED ANALYSES

### 10.2.1 Imaging Analysis

Pseudonymised participant MRI data will be sent electronically to the University of Edinburgh for analysis. The first MRI scan will serve as a baseline for comparison, and the pre-contrast imaging will serve as control for each scan individually. Images will be analysed using commercially available cardiac MRI software (Circle Cardiovascular Imaging software, cvi42®, Circle Cardiovascular Imaging Inc. Calgary, Alberta, Canada) through which myocardial contouring and T1 map creation and analysis is performed.

Analysis will be performed in the Image Analysis Core of the Edinburgh Imaging facilities. A standardised approach to T1 image analysis will be employed for manganese uptake [Singh et al, 2022]. Briefly, the basal, mid-cavity, and long axis T1 maps will be divided into segments according to the standard 17-segment model recommended by the American College of Cardiology/American Heart Association [Cerqueira et al, 2002]. After contouring epi- and endocardial borders and defining right ventricular insertion points, regions of interest will be derived for each of the 16 segments with a 10-20% epi- and endocardial offset to reduce risk of blood pool contamination. Manganese uptake will be quantified using a two-compartment Patlak model as described previously [Singh et al, 2022b], and this has excellent repeatability and reproducibility [Singh et al, 2023]. All image analysis will be performed blinded to group, timing and treatment allocation.

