## **14 STUDY CONDUCT RESPONSIBILITIES**

### **14.1 PROTOCOL AMENDMENTS**

Any changes in research activity, except those necessary to remove an apparent, immediate hazard to the participant in the case of an urgent safety measure, must be reviewed and approved by the Chief Investigator.

Proposed amendments will be submitted to the Sponsor for classification, review and authorisation.

Amendments to the protocol must be submitted in writing to the appropriate REC and local R&D for approval prior to implementation and prior to participants being enrolled into the amended protocol.

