### **14.2 MANAGEMENT OF PROTOCOL NON COMPLIANCE**

#### **14.2.1 Protocol Waivers**

Prospective protocol deviations, i.e. protocol waivers, will not be approved by the Sponsors and therefore will not be implemented, except where necessary to eliminate an immediate hazard to study participants. If this necessitates a subsequent protocol amendment, this should be submitted to the REC and local R&D for review and approval if appropriate.

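### Sections 6.5 and 8 of the protocol give two mangafodipir dosing rules for the same scan, a standard 5 mL and a per-kg dose, and do not say which governs.

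*Protocol*

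**What the plan says.** Section 6.5 (Imaging Contrast Media, Mangafodipir) describes a "0.05 mmol/mL solution for intravenous infusion" and gives the dose as a volume: "The standard dose of Mangafodipir will be 5ml although this will" depend on a comparison study still running at the Edinburgh hospital. There is no weight adjustment. The infusion is to last "approximately 10-15 minutes (0.4-1.2mL/min").

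Section 8, under Cardiac Magnetic Resonance Imaging with Manganese, describes how the scan is acquired. It gives the same agent from the same supplier as "mangafodipir (5 mmol/kg, 1 mL/min; IC Targets, Norway"), which is a dose per kilogram at a single rate.

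The scans supply the primary endpoint in section 2.2.1. Section 10.2.1 says: "Manganese uptake will be quantified using a two-compartment Patlak model as described previously". Neither section 6.5 nor section 8 refers to the other, and no precedence is stated.

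**The concern.** An intravenous dose should appear once, or identically wherever it appears. Here one section gives a volume that is the same for everyone and the other gives a volume that rises with body weight. A set volume and a per-kg dose can coincide at one weight only, so staff cannot follow both sections for most participants. The 1 mL/min in section 8 also does not fit the 5 mL and the duration in section 6.5.

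What is at stake is a clear instruction for an agent given at each imaging visit, and a uniform acquisition for the scan behind the primary endpoint. Sample size, randomisation and the planned comparisons are not affected.

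**Working it through.** **Inputs from the protocol.** Section 6.5: concentration 0.05 mmol/mL (50 µmol/mL), volume 5 mL, duration about 10–15 min, rate 0.4–1.2 mL/min. Section 8: 5 mmol/kg as printed, rate 1 mL/min.

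**Assumptions.** The protocol gives no mean body weight, so the weights below are illustrative. Reading the section 8 unit as µmol/kg is also an assumption.

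**1. Amount in the section 6.5 dose.** 5 mL × 0.05 mmol/mL = 0.25 mmol = 250 µmol. Per kilogram this is 250/50 = 5.0 µmol/kg at 50 kg, 250/70 = 3.57 at 70 kg and 250/100 = 2.5 at 100 kg.

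**2. Section 8 as printed.** At 70 kg, 5 mmol/kg × 70 kg = 350 mmol, and 350 / 0.05 = 7,000 mL. That is 7,000/5 = 1,400 times the section 6.5 volume and cannot be given.

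**3. Section 8 read as 5 µmol/kg.** 5 µmol/kg ÷ 50 µmol/mL = 0.1 mL/kg. The two rules agree where 0.1 × weight = 5 mL, that is at 50 kg.

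| Weight (assumed) | Section 6.5 | Section 8, as µmol/kg | Ratio |
|---|---|---|---|
| 50 kg | 5 mL | 5 mL | 1.0 |
| 60 kg | 5 mL | 6 mL | 1.2 |
| 70 kg | 5 mL | 7 mL | 1.4 |
| 80 kg | 5 mL | 8 mL | 1.6 |
| 100 kg | 5 mL | 10 mL | 2.0 |

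The conflict does not depend on the unit. For any per-kg dose d, agreement occurs only at the single weight 0.25 mmol ÷ d. With d as printed, that weight is 0.25/5 = 0.05 kg.

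**4. Rates against 5 mL over 10–15 minutes.** Rate = volume / time: 5/15 = 0.33 and 5/10 = 0.50 mL/min. The stated 0.4–1.2 mL/min is therefore not the range for 5 mL; the two overlap at 0.4–0.5 mL/min. Time = volume / rate for 5 mL:

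- 0.4 mL/min: 12.5 min
- 0.5 mL/min: 10 min
- 1.0 mL/min (the section 8 rate): 5 min
- 1.2 mL/min: 4.2 min

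Section 8's own dose at its own rate, under the µmol reading, takes 7 min at 70 kg, 10 min at 100 kg and 15 min at 150 kg. It falls short of 10 minutes for anyone under 100 kg.

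**5. Whether the rate range shows which rule was meant.** Rates of 0.4–1.2 mL/min deliver 4–12 mL in 10 minutes and 6–18 mL in 15 minutes. That covers 5 µmol/kg over 10 minutes for 40–120 kg. It also covers another set volume: 10 mL over 10–15 minutes needs 0.67–1.0 mL/min. The range cannot decide between the rules.

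**The case against.** The strongest reply is that section 6.5 is the dedicated contrast section, calls 5 mL the standard dose and openly makes it provisional. A reader would naturally start there. If the volume may change, a generous rate range is loose drafting and need not be an arithmetic error. The range does contain rates that suit 5 mL. This much stands: one might infer that most of the stated rates are wrong, but a range that may allow for other volumes does not support that. The firm mismatch is section 8's 1 mL/min against 5 mL.

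The unit may also be an artefact of reading the PDF. The µ sign came through intact in section 6.5, but that does not settle what section 8 prints. The 7,000 mL figure therefore shows only that mmol cannot be meant; it does not describe an overdose that anyone would give.

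A reader might go further and infer that the primary endpoint or the treatment comparison is biased. The documents do not support this. Applied consistently, either rule treats the randomised arms alike and gives a participant of stable weight the same volume at each scan. Section 10.2.1 uses pre-contrast imaging as the control for each scan. Nothing in the protocol shows how the Patlak estimate responds to dose, so an effect is possible but not shown.

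The reply does not remove the conflict itself. A proviso about a future change does not reconcile a set volume with a per-kg dose in the current text. Any change is already controlled: section 14.1 says "Amendments to the protocol must be submitted in writing to the appropriate REC and local R&D for approval prior to implementation", and section 14.2.1 says "Prospective protocol deviations, i.e. protocol waivers, will not be approved by the Sponsors and therefore will not be implemented". The text in force therefore has to be one that staff can follow.

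**Conclusion.** The protocol is wrong as written, with minor severity. Two sections give different dosing rules for one infusion, and nothing reconciles them. That conclusion holds under either unit.

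Its size rests on the µmol/kg reading and on assumed weights: no difference at 50 kg, 1.4-fold at 70 kg and 2-fold at 100 kg. Separately, and whatever the unit, section 8's rate delivers the section 6.5 volume in 5 minutes, half the stated minimum of about 10. Within the section 6.5 range only 0.4–0.5 mL/min suits 5 mL, although the wider range may be there for other volumes.

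The finding is confined to an inconsistent instruction. No harm to participants has been quantified.

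**What to change.** State one dosing rule in both sections, as the sponsor and pharmacy decide, with a rate and duration that agree with it. Call it the current standard dose, and say that any change following the comparison study will come through a formal amendment.

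- If a set volume: 5 mL over 10–15 minutes, at 0.33–0.50 mL/min.
- If per kg: 5 µmol/kg, which is 0.1 mL/kg, over 10–15 minutes. That is 0.40–0.60 mL/min at 60 kg, 0.47–0.70 at 70 kg and 0.67–1.00 at 100 kg.

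Check the source document for section 8. If it does print mmol/kg and the per-kg rule is kept, correct the unit to µmol/kg. Replace the 1 mL/min in section 8 with a rate that fits the chosen rule. A sentence keeping one dosing rule across all of a participant's scans would be a useful but optional addition.

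The cost is a wording amendment to two paragraphs, with no extra participants, scans or data fields.
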